Our primary outcome is radiographic evidence of fracture healing at the 12-week endpoint. At 4, 8 and 12 weeks after initiating TPTD or TPTD placebo, all patients will get follow-up pelvic radiographs, although these radiographs will stop when healing occurs. If the radiologist notes cortical bridging on the monthly x-ray, or at 3 months a confirmatory limited low dose Focus CT at the fracture site(s) will be performed to assess the degree of bridging. Cortical bridging will be quantified with bridging of 3 or 4 cortices as "healing", 1 or 2 cortices as "partial healing", and 0 cortices as "minimal/no healing" by two independent radiologists and adjudication by a third. If there are multifocal fractures, cortical bridging at each site will be evaluated and an adjudicated score representing the state of healing (0 to 4) will be recorded. Secondary analysis will examine treatment group differences in the change in follow-up pelvic fracture healing scores over the repeated monthly assessments during the 3 month placebo-controlled phase.

A secondary outcome is pain and narcotic use. The numeric rating scale (NRS) will be administered by research staff that is blinded to treatment group. We will also quantify use of narcotics and other adjunct medications for pain by recording their reported use and also asking for narcotic bottles to be brought in at each visit and performing a pill count. The NRS and recording of pain medications will be done at baseline, 4, 8 and 12 week visits and at the 6, 9 and 12 month visits.

Another secondary outcome is lower extremity physical function at 3 months and again from 3-12 months. Physical performance tests will be administered by research staff that is blinded to treatment group. The lower extremity physical function tests, tests include normal walking speed over 4 meters (with or without an assistive device), repeated chair stands (stand up from a chair with their arms folded across their chest), and balance (ability to maintain balance for 10 seconds in each of 3 positions: side-by-side, semi-tandem, and tandem foot positions). In addition, the Timed Up and Go test will be completed by each subject. Each subject will also complete the survey of ADLs and the SF-36.

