For the secondary outcome of pain, we will use a between-groups linear mixed model for repeated measures (LMMrm) to estimate the between-group difference in the mean within-subject change from baseline to the end of the placebo controlled trial (0-3 months) and again to explore change from 3 to 12 months in the open label extension. Narcotic and non-narcotic pain medication use will enter the model as time-dependent covariates. Separately, treatment group differences in the cumulative narcotic and non-narcotic drug exposure in the 3-month placebo-controlled phase will also be estimated with linear mixed model for repeated measures. This analysis addresses the two questions, “Do patients treated with TPTD show more rapid reduction in reported pain level than those not so treated? If so, when?”

For the secondary outcome of lower limb physical function, we will use a between-groups linear mixed model for repeated measures (LMMrm) model for the analysis to estimate the difference in within-subject change from 0 to 3 months in the CSPP score in the two groups. A secondary analysis for this aim will explore the changes in physical function from 3 to 12 months in the two groups.

If TPTD can improve fracture healing, this study will have an impact on the treatment of persons with pelvic fracture who are not surgical candidates and often face severe pain, chronic immobility, and loss of function in the elderly. A positive finding of accelerated healing of pelvic fractures would also encourage study of TPTD for treatment of other osteoporotic fractures.

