fracture patients given 1-84PTH were healed within 12 weeks compared to 68% of the controls. However, there is not sufficient evidence at this time to recommend routine use of PTH peptides for fracture healing. Pelvic fractures are ideal to study for the impact of Teriparatide (TPTD) on rate of fracture healing because there are no surgical repairs for the vast majority of the fractures. Prior studies of TPTD on wrist fracture healing were limited and confounded by the increased prevalence of surgical fixation to treat these fractures. Strong evidence of pelvic fracture healing that may result from this study may not only have an impact on pelvic fractures but perhaps may indicate a potential use for other fractures as well.

In our proposed randomized, double blind, placebo controlled clinical trial in patients >65 years of age with acute pelvic fracture, we plan to evaluate whether treatment with daily subcutaneous TPTD 20 mcg/day compared with placebo, in addition to standard treatment (pain management, bed rest and prevention of complications from comorbid conditions), is effective in accelerating fracture healing in women and men compared to standard treatment alone. We hypothesize that development of a successful adjunctive therapy (TPTD) will accelerate radiographic evidence of fracture healing and speed functional recovery. If this hypothesis holds true, it would lead to a change in clinical practice and an improved quality of care for pelvic fracture patients. Evidence of an impact on the healing of pelvic fractures may also extend to a potential to improve healing of other osteoporosis-related fractures. In the planned trial we will recruit women and men with acute pelvic fractures and address 3 specific aims over 3 months of treatment in a placebo controlled double blind study to determine if **TPTD** in addition to standard care **versus placebo** and standard care:

1. Results in **earlier evidence of cortical bridging** on routine radiographs followed by confirmatory Focus CT, a novel method to reduce radiation exposure from CT scans (primary outcome).
2. Leads to **a faster reduction in pain** as assessed by both the Numeric Rating Scale and a reduction in the use of narcotics (secondary outcome).
3. Leads more to a more rapidly **improved functional outcome** using a short physical performance battery to assess lower extremity function (secondary outcome).

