**Screening visit:** At the screening visit, a Mini Mental Status Exam (MMSE) will be given to be sure that the patient is capable of providing informed consent and of completing the trial. Any persons with moderate or severe cognitive impairment will be excluded (score  $\leq$ 18 of 30 points). The consent form will be reviewed and signed. A comprehensive assessment of medical history and a brief physical exam will be performed. Blood samples will be obtained and levels of creatinine, alkaline phosphatase, calcium, intact-parathyroid hormone, and 25(OH)D will be measured. Pelvic radiographs and a full CT scan will be reviewed or obtained to determine if fractures are: single rami, multiple rami fractures or sacral and pelvic fractures (healing of sacral fractures will not be assessed, although the existence of a sacral fracture with a pubic rami fracture will not exclude an individual). In addition, the fracture will be classified by amount of displacement/overriding with 3 categories: Minimal/No displacement, Mild displacement, Moderate displacement. A loading dose of vitamin D (50,000 IU) will be given in order to normalize vitamin D in this population with high prevalence of vitamin D deficiency before initiating treatment (goal within 2 weeks of the fracture). Serum calcium must be below or equal to normal for the lab. Calcium supplements or dietary modifications will be recommended as needed to bring total calcium intake to approximately 1000 mg daily. Subjects who meet all inclusion and exclusion criteria based on labs and history will be scheduled for a baseline visit. Concomitant medications and existing baseline conditions will be collected by interview. Information about the use of prior osteoporosis treatment will be obtained and recent BP use will be categorized for randomization.

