**Follow-up visits:** All visits will occur at the center where the subject was recruited and would normally be seen, following the schedule of procedures listed in Table 2. Visits will occur every month for 3 months. At every visit a pelvic radiograph will be taken. If the radiologist notes cortical bridging on pelvic x-ray, then a confirmatory low dose Focus CT at the fracture site(s) will be performed to assess the degree of bridging at the

fracture site(s). If full union is noted at the superior and/or inferior pubic fracture site(s) by focus CT, as evaluated by both radiologists, then no further radiographs or CT scans are needed, although all other assessments will continue. The CT will be done at either Ramapo Radiology in Suffern or MRI in New City, NY. At 3 months the remaining patients who still have not healed will undergo a focused limited low dose CT to quantify the degree of cortical bridging at the end of the 3 months of placebo-controlled treatment. In addition, radiographic follow-up will continue during the open label extension for those patients who have not healed during the 3 month active treatment phase.

Blood samples to assess bone turnover and calcium levels will be collected as indicated. Subjects will be encouraged at each visit to consume enough calcium and vitamin D (1000 IU vitamin D and dietary calcium with supplements as needed) and TPTD/placebo compliance will be assessed.

At each monthly visit (0 to 3), subjects will complete the lower extremity physical function test, ADLs, SF-36, NRS for pain and a narcotic use survey and pill count (details below). This information will be recorded by a research nurse blinded to treatment status since TPTD and placebo will be identical in appearance. Lower extremity physical function test, ADLs, SF-36, NRS for pain and a narcotic use survey and pill count will be repeated at 6, 9 and 12 months visits to determine if starting TPTD immediately after fracture results in better long term changes in function and pain, although the extension will be open label with all offered TPTD and analyzed as a separate secondary outcome (3 to 12 month; see below).

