**Table 2: Schedule of Procedures**

Procedure	SCR	D1	4 wk	8 wk	12 wk	6 mo	9 mo	12 mo
MMSE, Informed consent	X							
Medical history, medication list and other lifestyle	X							
Physical examination, including height and weight	X							
Screening labs (25(OH)D, PTH, Cr, Ca, prior alkaline phosphatase)	X							
Pelvic radiographs (^until healing occurs-standard care)	X		X^	X^	X^			
Pelvic limited focus CT scan (* as indicated based on cortical bridging and until healing occurs)	X full		X*	X*	X*			
Bone turnover		X	X	X	X			

Calcium for safety		X	X	X	X	X	X	X
Loading dose vitamin D (50,000 IU)	X							
Calcium (total intake 1000 mg) /1000 IU vitamin D		X	X	X	X	X	X	X
Dispense TPTD 20 mcg/day or placebo (blinded for 3 months, then open label TPTD)		X	X	X	X	X	X	X
Adverse event and concomitant medications		X	X	X	X	X	X	X
Numeric Rating scale (NRS) for pain and narcotic use survey and pill count		X	X	X	X	X	X	X
Lower extremity physical function (CSPPS and TUG)		X	X	X	X	X	X	X
Self-reported questionnaires (ADL and SF-36)		X	X	X	X	X	X	X
Telephone calls will occur weekly			X	X	X			

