**Statistical Plan:** There will be no interim analysis and missing outcome data will not be imputed. Statistical analysis will be performed using SAS software (Cary NC). Between group differences at baseline will be compared with t-tests or Wilcoxon rank sum tests and chi-square tests as appropriate (p-value <0.05 for significance). Randomization by the method of randomly permuted blocks will be created for gender and BP use groups. Our primary analysis is ITT analysis and our primary outcome (SA#1) is the categorization of the level of bridging seen on focus CT into the scores from 0 to 4, described above between 0 and 3 months. The difference in cortical bridging will be evaluated by a 2x5 chi-square (group x score) with a trend test (Jonckheere-Terpstra) to see whether TPTD treated "trend" to have more higher bridging scores than the placebo group. We expect 30% - 50% superiority with TPTD at 3 months. This categorical outcome will be further analyzed with generalized estimating equations (GEE) for longitudinal repeated measures assuming a Poisson distribution with weighting from logistic regression analysis of the missingness pattern. Secondary analyses of covariates, sensitivity analyses and the "per protocol" analysis will incorporate the aforementioned approach into this aim's GEE analysis. This analysis addresses the question "Do patients treated with TPTD show more rapid fracture healing than those given placebo? For SA #2, we anticipate that the difference in pain score between the TPTD and placebo groups in the proposed study will be > 30% at each monthly time point (0-3 months). We will use a between-groups linear mixed model for repeated measures (LMMrm) to estimate the primary outcome of the difference in the mean within-subject change from baseline in the two groups at the end of the placebo controlled trial (0-3 months) and again to explore change from 3 to 12 months in the open label extension. In addition, narcotic and non-narcotic pain medication use will enter the model as time-dependent covariates. This analysis addresses the two questions, "Do patients treated with TPTD show more rapid reduction in reported pain level than those not so treated? If so, when?" For SA#3, the CSPPS is the outcome. A linear mixed model for repeated measures (LMMrm) will be used with fixed effects of treatment group (TPTD vs. placebo), time (D1, 4-, 8- and 12-wk) and their interaction, the baseline level of the CSPPS and days from injury to randomization entered as covariates, and a within-subject covariance structure selected by empirical methods prior to hypothesis testing. This plan will be repeated for the "per protocol" analysis in which subjects are limited to those showing 80% or greater compliance over the 12-week trial. This statistical plan addresses the two clinical questions, "Do patients treated with TPTD recover lower limb function faster than those not so treated? If so, when?" LMMrm will be used to analyze data from 3-12 months and assess group by time interaction. We will group on prior BP exposure strata to account for possible heterogeneity in the R-side covariance structure.

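### The only NRS pain model written out adjusts for post-randomisation analgesic use, which is itself part of Aim 2, so it need not estimate the TPTD-placebo difference it names

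*Combined protocol and SAP*

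**What the plan says.** The Protocol Summary and the Statistical Plan (section 7) describe one linear mixed model for NRS pain. Its stated target is the contrast between arms in average NRS change from baseline over 0-3 months, and its stated purpose is to learn whether reported pain falls faster on TPTD, and when. Into that model goes medication use: "Narcotic and non-narcotic pain medication use will enter the model as time-dependent covariates". The Statistical Plan repeats the sentence, opening it with 'In addition'. It also expects that "the difference in pain score between the TPTD and placebo groups in the proposed study will be > 30" per cent at every monthly visit.

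On timing, the Protocol Summary says "The NRS and recording of pain medications will be done at baseline, 4, 8 and 12 week visits". The Follow-up visits text in section 4 collects "SF-36, NRS for pain and a narcotic use survey and pill count (details below" at each monthly visit, and Table 2 puts both on one row: "Numeric Rating scale (NRS) for pain and narcotic use survey and pill count".

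On the role of drug use, aim 2 in section 2 defines the pain outcome "as assessed by both the Numeric Rating Scale and a reduction in the use of narcotics (secondary outcome"). The Protocol Summary also plans a model with drug use as the outcome: "Separately, treatment group differences in the cumulative narcotic and non-narcotic drug exposure in the 3-month placebo-controlled phase will also be estimated".

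**The concern.** Analgesic use at weeks 4, 8 and 12 arises after treatment starts, and the trial hypothesises that TPTD will reduce narcotic use. The plan therefore adjusts one half of Aim 2 for the other half. If TPTD lowers use, and use is related to reported pain within arms, the group coefficient no longer estimates the difference in average NRS change that the plan names. The plan states no conditional or direct-effect target and gives no reason for adjusting. It also does not say whether use is coded as current, lagged or cumulative.

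The covariates named for the SA#3 function model are all fixed before randomisation: baseline CSPPS and the time between injury and randomisation. At stake is whether the published answer on pain is the answer to the question asked. It could be too small, about right or too large.

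**Working it through.** The documents give no NRS standard deviation, no correlation between analgesic use and NRS, and no power for pain. There is no planned figure to reproduce. The algebra below shows what the adjusted coefficient estimates; every numerical input is an assumption unless marked otherwise.

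**1. One visit.** Let Δ be the unadjusted TPTD-placebo difference in NRS, D the effect of TPTD on analgesic use, and β the within-arm slope of NRS on use. Then

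adjusted effect = Δ − β × D.

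This equals Δ only if β = 0 or D = 0. With narcotic and non-narcotic use entered separately, β × D becomes a sum of two such products, and equality could also arise by cancellation.

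**2. Size in observable terms.** Inputs: placebo NRS mean 5 and SD 2 (assumed); Δ = −0.30 × 5 = −1.5 (the 30% is from the Statistical Plan); D = −0.5 SD of use (assumed); ρ = within-arm correlation of use with reported NRS. Then β × D = ρ × 2 × (−0.5) = −ρ, so the adjusted effect is −1.5 + ρ.

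| ρ | adjusted effect | ratio to −1.5 |
|---|---|---|
| 0.6 | −0.90 | 0.60 |
| 0.4 | −1.10 | 0.73 |
| 0.2 | −1.30 | 0.87 |
| 0 | −1.50 | 1.00 |
| −0.2 | −1.70 | 1.13 |
| −0.4 | −1.90 | 1.27 |

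At ρ = 0.4, D = −0.25 SD gives −1.5 + 0.4 × 2 × 0.25 = −1.30 (ratio 0.87). D = −0.75 SD gives −1.5 + 0.4 × 2 × 0.75 = −0.90 (ratio 0.60).

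**3. Why the sign of ρ is open.** Patients in more pain take more drug, and the drug lowers reported pain. Write underlying pain as L, use as M = aL + u, and NRS = L − bM + e, with SD(L) = 2, SD(e) = 1 and TPTD shifting L by −1.5. Then

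- unadjusted = −1.5(1 − ab)
- adjusted = −1.5(1 − r²), where r² = 4a² / (4a² + SD(u)²) is the squared correlation of M with L.

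| a, b, SD(u) | r² | correlation of use with NRS | unadjusted | adjusted | ratio |
|---|---|---|---|---|---|
| 0.5, 0, 1 | 0.50 | 0.63 | −1.50 | −0.75 | 0.50 |
| 0.5, 0.5, 1 | 0.50 | 0.38 | −1.125 | −0.75 | 0.67 |
| 0.5, 0.3, 2 | 0.20 | 0.11 | −1.275 | −1.20 | 0.94 |
| 0.5, 0.8, 3 | 0.10 | −0.66 | −0.90 | −1.35 | 1.50 |

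Nine such settings were examined. The ratio was 0.50-0.67 where use tracks pain closely, 0.94-1.07 where use is nearly uncorrelated with reported NRS, and 1.30-1.50 where heavier users report less pain. The result also depends on the assumed spread of pain. For a = 0.5, b = 0.3, SD(u) = 1 the ratio is 0.75/1.275 = 0.59 with SD(L) = 2. With SD(L) = 1.25, r² = 0.39/1.39 = 0.28, adjusted = −1.08, and the ratio is 0.85.

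**4. Repeated measures.** Large simulated trials with visits at weeks 4, 8 and 12, baseline NRS as covariate and unstructured covariance lead to the same conclusion.

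- With a from 0 to 0.8 and a drug effect of 0 to 1.0 point per unit, the model without analgesic covariates recovered the total week-12 effect within 0.02 points in every setting.
- With the covariate, a total effect of −1.275 (a = 0.5, drug effect 0.3) became −0.56 or −1.08, for noise SD in use of 0.5 or 1.0. A total of −0.75 (a = 0.5, drug effect 1.0) became −0.52 or −1.05.
- With a = 0, so that TPTD does not change use, both models gave −1.50 to within 0.01.
- Coding matters. Over the nine settings of step 3, the week-12 ratio ran from 0.54 to 1.52 with concurrent use as covariate and from 0.24 to 1.76 with cumulative use.
- With no TPTD effect on pain or drug use, all estimates lay within 0.01 of zero.

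**The case against.** The strongest reply is that 'In addition' in the Statistical Plan marks a second step after a complete base model, and that the later covariate paragraph places other covariates in secondary analyses or tests them before inclusion. That reading is tenable. But both places say that use enters the model, the Protocol Summary has no softening words, the analgesic terms are unconditional, and no NRS contrast without them is promised. At best the plan supports two readings.

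Second, every patient receives pain management, so unadjusted NRS is pain under analgesia, and wanting pain net of drugs is reasonable. In three of the nine settings the adjusted estimate is indeed nearer the assumed underlying effect of −1.5 (for example −1.35 against −0.90). In the other six it is further away (for example −0.75 against −1.125), so adjustment is not a dependable correction for masking. The plan also asks about reported pain.

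Third, the separate exposure analysis will show any difference in drug use. That lessens the harm and covers the narcotic half of Aim 2, but it yields no NRS contrast.

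Finally, the numbers rest on assumed inputs and span a wide range. That is correct: they show that the gap can matter in either direction, not how large it will be in this trial.

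**Conclusion.** The concern holds. As written, the NRS model conditions on a post-randomisation outcome of the same aim, and its group coefficient need not equal the difference the plan names. The two agree if TPTD does not change analgesic use or if use is unrelated to reported NRS; otherwise they agree only by coincidence. The documents cannot fix the size or direction: under the assumptions shown, the effect may shrink, hardly move or be exaggerated. Pain is a secondary outcome with no power claim and the bridging analysis is untouched, so this should be corrected but does not threaten the trial's main conclusion.

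**What to change.** Make the main SA#2 analysis the 0-3 month NRS repeated-measures model without post-randomisation analgesic covariates. Baseline NRS and baseline analgesic use may be included; state whether baseline NRS enters as a covariate or as a response, and which NRS item (current or past-week average) is analysed. Report the result beside the planned analysis of cumulative narcotic and non-narcotic exposure. Keep the medication-adjusted model as a labelled exploratory analysis with the coding of use stated.

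As a clarification, say which record the candidate covariate for concomitant medications refers to. The Screening visit text says "Concomitant medications and existing baseline conditions will be collected by interview", but Table 2 also records them through follow-up. For the main NRS model it should be the screening record.

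The cost is SAP wording; all variables are already collected. The downside is that the estimate reflects pain under the analgesics actually taken, so heavier use on placebo can hide part of a difference. With a = 0.5 and analgesics lowering reported pain by 0.5 point per unit, an underlying −1.5 appears as −1.5 × (1 − 0.25) = −1.125. The NRS result must therefore be read together with the drug-exposure result.

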## **2. Trial Objectives and Purpose:**

By 2030 over 25% of the entire US population will be older than 65 years of age. Pelvic fracture rates are higher in women Over 90% of pelvic fractures in patients >60 years are defined as osteoporosis related fractures. In a recent study in Germany, the rate of all first pelvic fractures in persons over 60 was 22.4 [95% CI 22.0–22.9] per 10,000 person-years. The incidence rate increases dramatically with age, from 5.4 and 3.8 per 10,000 person-years in women and men aged 65 to 69 years to 93.5 and 44.5 per 10,000 person-years in women and men aged 90 years and older, respectively. This is in agreement with studies in the US and Finland, also showing an increase in incidence of pelvic fractures with age. Pelvic fractures are most often a result of low-energy trauma, such as a fall from standing height. Pelvic fractures are the most relevant for this proposed randomized placebo controlled study. This fracture is accompanied by severe pain, chronic immobility and loss of function and independence in the elderly. The current treatment strategy of pelvic fractures includes pain management, patient mobilization, and the prevention of complications associated with comorbid conditions. In a review of six studies with over 500 patients, the mean length of hospital stay was 13.4 days and the average 1-year mortality was 16.3%. Mortality rates in 1300 pelvic fracture patients were still elevated at 3 years. Pelvic fractures are associated with slow healing and a delayed return to full function and normal activity. Pelvic fractures consume substantial healthcare resources, and based on administrative claims data, they are one of the most costly osteoporosis related fractures. Un-healed fractures, occurring in one-third of pelvic fracture patients at 3 months, can cause continued pain and impact mobility. With aging of the population, and expected concomitant increase in the incidence of pelvic fractures, there is a pressing need to find effective treatments that will accelerate healing. There are strong preclinical data as well as clinical evidence that administration of parathyroid hormone (PTH) peptides may improve bone union, hasten fracture healing and improve physical function. In one nonrandomized, un-blinded study, 100% of pelvic

fracture patients given 1-84PTH were healed within 12 weeks compared to 68% of the controls. However, there is not sufficient evidence at this time to recommend routine use of PTH peptides for fracture healing. Pelvic fractures are ideal to study for the impact of Teriparatide (TPTD) on rate of fracture healing because there are no surgical repairs for the vast majority of the fractures. Prior studies of TPTD on wrist fracture healing were limited and confounded by the increased prevalence of surgical fixation to treat these fractures. Strong evidence of pelvic fracture healing that may result from this study may not only have an impact on pelvic fractures but perhaps may indicate a potential use for other fractures as well.

In our proposed randomized, double blind, placebo controlled clinical trial in patients >65 years of age with acute pelvic fracture, we plan to evaluate whether treatment with daily subcutaneous TPTD 20 mcg/day compared with placebo, in addition to standard treatment (pain management, bed rest and prevention of complications from comorbid conditions), is effective in accelerating fracture healing in women and men compared to standard treatment alone. We hypothesize that development of a successful adjunctive therapy (TPTD) will accelerate radiographic evidence of fracture healing and speed functional recovery. If this hypothesis holds true, it would lead to a change in clinical practice and an improved quality of care for pelvic fracture patients. Evidence of an impact on the healing of pelvic fractures may also extend to a potential to improve healing of other osteoporosis-related fractures. In the planned trial we will recruit women and men with acute pelvic fractures and address 3 specific aims over 3 months of treatment in a placebo controlled double blind study to determine if **TPTD** in addition to standard care **versus placebo** and standard care:

1. Results in **earlier evidence of cortical bridging** on routine radiographs followed by confirmatory Focus CT, a novel method to reduce radiation exposure from CT scans (primary outcome).
2. Leads to **a faster reduction in pain** as assessed by both the Numeric Rating Scale and a reduction in the use of narcotics (secondary outcome).
3. Leads more to a more rapidly **improved functional outcome** using a short physical performance battery to assess lower extremity function (secondary outcome).

Although our primary analysis will be based on data from 0 to 3 months, whether the benefit of TPTD on fracture healing wanes over time is unclear, making a longer follow-up important to extend our knowledge on the persistence of early TPTD effect on these outcomes. Therefore, we will extend this study with 9 months of open label TPTD to determine if any potential differences between the placebo and TPTD groups during the 3 months of treatment are evident and persist over time, even in patients who use TPTD after the three month placebo controlled intervention.

If TPTD can improve fracture healing, this study will have an impact on the treatment of persons with pelvic fracture who are not surgical candidates and often face severe pain, chronic immobility, and loss of function in the elderly. A positive finding of accelerated healing of pelvic fractures would also encourage study of TPTD for treatment of other osteoporotic fractures.

